7.1.2 Investigational Medicinal Product rituximab

Rituximab is commercially available for administration as a concentrate for solution for infusion. The concentrate is presented as two strengths: 100 and 500 mg.

Rituximab will be considered the IMP for the purposes of the trial during the second stage of the trial (6 patient safety cohort). Rituximab should be taken from standard hospital stock.

Patients receiving rituximab treatment are at risk form developing progressive multifocal leukoencephalopathy (PML). Patients should be closely monitored for new or worsening neurological, cognative or psychiatric signs or symptoms which may be suggective of PML. It is also good practice to advise patients to inform their partners/caregivers about their treatment since they may notice symptoms that the patient in not aware of.

If PML is suspected rituximab treatment must be suspended. Treatment can be recommence if PML is excluded.

The IMP will need to be labelled in accordance with local regulations and Good Manufacturing Practice (GMP), stating that the drug is for clinical trial use only. A label will be provided by the Trials office for this purpose. For further details and instructions, please refer to the pharmacy manual.

7.2 Treatment Schedule

AZD2014 is to be administered twice daily orally on an intermittent schedule at a dose of 125mg. Two consecutive days of treatment will be followed by 5 days with no treatment each week. Treatment would therefore be on days 1, 2, 8, 9, 15, 16, 22 and 23 of each cycle of 28 days. Treatment days should be two consecutive days and should be the same days each week, for example if treatment was started on a Monday in the first week further treatments would be expected to continue to be on Mondays and Tuesdays each week. Treatment will continue until progression or withdrawal due to toxicity or due to patient choice.

For the second, combination, stage of the trial, rituximab 375mg/m² will also be administered intravenously in the standard fashion as per local protocol on day 1 of the 28 day cycle for a total of 6 cycles. Pre-medication with antihistamines (e.g.Piriton), hydrocortisone and paracetamol is permissive as per local protocols for use of rituximab in the 6 patient combination stage.

Where possible all doses of AZD2014 should be taken at approximately the same times each day. AZD 2014 doses can be taken with or without food. Twice daily doses should be taken approximately 12 hours apart. If vomiting occurs within 30 minutes after AZD2014 dosing, or if the tablet(s) can be identified in the vomit content, the patient can re-take new tablet(s).

If a patient misses a dose and remembers within 2 hours, they should take the dose straight away and continue to take the rest of their medication as planned. If a dose is missed and the patient remembers after 2 hours or longer, they should take the next dose when it is due

7.3 Assessments

	Screening	Cycle1-2 (28 day cycles)		Cycle 3- 6 (28 day cycles)		End of 6 cycles	Cycles 6+ (28 day cycles)	End of Treatment	30 Day Follow-up (+/- 5 days)	3 monthly follow-up	1 year post start of treatment
		Day 1	Day 15	Day 1	Day 15		Day 1				
Informed consent	Х										
Inclusion/Exclusion Criteria	х										
Pregnancy Test	Х	X ^a									
Medical History	Х										
Clinical assessment ^b	Х	Х	Х	Х			Х	Х	Х	Х	
Constitutional symptoms	Х	Х	Х	Х			Х	Х			
ECOG Performance Status	Х	Х		х			Х	x	Х		
Clinical Chemistry/haematology/ cardiac markers) ^c	х	Xď	Xď	Xď			Xď	Xe	X ^e		
Echocardiology/ MUGA ^f	Х										
Urinalysis	Х										
12 lead ECG ^g		X ^h		X ^h			X ^h	Х			
CT Scan (NCAP) ⁱ	Х		Xi		Xi	Xi	Xi	X ^j		X ^j	X ^{ij}
PET	Х		X ^k			X ^k		X		X	
AZD2014 Treatment					<< 2	X ^m >>		1			
Rituximab Treatment		Х		Х							
Dosing compliance		Х	Х	Х	Х	Х	Х	Х			

Adverse events		< <throughout study="">>ⁿ</throughout>							
Concomitant medications			< <throughout study="">></throughout>						
Blood for research ^o	Х	Х		Х	Х				
Tumour biopsy	X ^p	X ^q				Xp			
Saliva sample	X ^r								

a) Within 7 days prior to cycle 1 day 1

b) Clinical assessment to include vital signs (heart rate, systolic and diastolic BP, oxygen saturation (pulse oximetry), , height (screening only), weight, and temperature Constitutional symptoms will include, night sweats and recurrent fever ≥38.0°C, (a history of weight loss is to be collected at screening visit only).

- c) Laboratory tests to include full blood counts, Standard biochemistry including glucose (fasted at screening only), Hba1c, triglycerides and cholesterol Cardiac markers Troponin (isoform as per institutional norm), LDH and AST should be assessed at screening and pre-dose on first day of treatment.
- d) Up to 3 days prior

e) All patients with clinically significant abnormal laboratory results at treatment completion or study drug discontinuation visit are to be followed until the results return to normal (or patient's baseline), or until a valid reason, other than a drug-related effect, is identified.

- f) Echocardiography should also be carried out if a patient develops signs and/or symptoms suggestive of a deterioration in LVEF or in case of the pre-specified ECG finding
- g) An ECG should be performed at any cardiac event with symptoms that may be due to cardiac ischemia, or arrhythmia (such as chest pain or palpitations). An ECG is also required in all cases of dyspnoea and pulmonary oedema.
- h) In the monotherapy study ECGs are to be taken on cycle 1 day1 Pre dose and cycle 1 day1, 2hrs post dose. The ECG should be taken on day 1 of subsequent cycles only in instances where the cycle 1 day 1 ECGs were abnormal. In the combination study ECGs should be taken on day 1 cycle 1 pre and post dose and day 1 of each subsequent cycle until indicated otherwise.
- i) CT at the end of every 2 cycles for first 6 cycles, then every 4 cycles (or if clinical suspicion of progression) and at 1 year post treatment start if not progressed on treatment. High resolution CT of the chest should be performed if clinically indicated by pulmonary symptoms any time during the study.
- j) If no longer receiving treatment, every 3-4 months for 1 year from treatment start and / or at clinical suspicion of progression
- k) The cycles 2&6 PET-CT scans should be performed in the 5 day gap between treatments on days 17-21 but ideally as close to the next administration of treatment i.e. days 20/21 to avoid the potential for inflammatory uptake of FDG
- I) Only if disease progression suspected
- m) Treatment will be delivered on a 2 days on 5 days off schedule until disease progression, unacceptable toxicity or patient choice.
- n) Patients with an unresolved adverse reaction (AR) or SAE event at treatment completion or study drug discontinuation will be monitored until the event is resolved, stabilised or the patient is lost to follow up.
- o) (OPTIONAL) Screening, end of cycle 2, end of cycle 6 and/or at progression. Additional samples will be taken in responding patients every 3 months for up to a year
- p) Within 3 months of trial entry and at relapse, mandatory. May include bone marrow if indicated for disease staging.
- q) Optional biopsy on day 15 of cycle 1
- r) To be taken from patients who have consented to the optional sub study which requires the collection of additional blood and saliva samples

Additional optional assessments may be performed at the discretion of the investigator if clinically indicated or in the event of toxicity.

7.3.1 Blood chemistry, Haematology and cardiac markers

Blood tests should be collected at the following timepoints (+/-3 days)

Clinical chemistry and haematology laboratory tests

- o Screening
- Cycles 1-2 (days 1 and 15)
- o Cycle 3 onwards (day 1)
- o End of treatment
- 30 day follow-up visit

Tests should include full blood counts, standard biochemistry including glucose, HbA1c, triglycerides and cholesterol.

Cardiac markers; Troponin (isoform as per institutional norm), plus LDH and AST/ALT should be assessed at screening and pre-dose on first day of treatment.

Troponin (or additionally other cardiac markers, i.e. AST/ALT and LDH depending on the Investigators decision if clinically indicated) should also be assessed on identification of abnormal ECG findings, e.g. new repolarisation abnormalities, found to be possibly clinically significant by investigators judgement. A repeat cardiac marker assessment should also be performed 24 hours later if such changes have been observed. The same Troponin isoform should be assessed at each of the visits (see IB for more detailed information).

An unscheduled serum urea and creatinine test should be performed in every case of diarrhoea that is categorised as a serious adverse event (SAE).

7.3.2 Clinical/symptom assessment

A clinical assessment including vital signs (heart rate, systolic and diastolic BP, oxygen saturation (pulse oximetry), and temperature will be performed at:

- Cycles 1-2 (days 1 and 15)
- Cycles 3 onward (day 1 of every cycle)
- End of Treatment Visit,
- 30 day Follow-up Visit.

Constitutional symptoms will be collected during cycles 1-2 (day 1 and 15), cycle 3 onwards (day 1), and End of Treatment Visit.

Constitutional symptoms will include the, night sweats, weight loss and recurrent fever ≥38.0°C in the absence of infection,.

7.3.3 ECG

ECGs should be taken on cycle 1 day 1 pre dose and, 2 hrs post dose .If the cycle 1 day 1 ECG taken as part of the monotherapy study is abnormal then ECG measurements should be taken on day 1 of all subsequent cycles. During the combination study ECGs should be taken on cycle 1 day 1 pre dose and, 2 hrs post dose and day 1 of all subsequent cycles unless indicated otherwise.

Twelve-lead ECGs will be obtained after the patient has been resting semi-supine for at least 10 minutes. All ECGs should be recorded with the patient in the same physical position. For each time point 1 ECG recording should be taken.

If an abnormal pre dose ECG finding is considered by the Investigator to be clinically significant, it should be reported as a concurrent condition. During the study, clinically significant abnormal ECG findings not present at pre dose should be reported as an AE. If present, the clinical signs and symptoms associated with the abnormal finding should be reported as the AE with the ECG abnormality given as explanatory information. Further ECGs should be performed until recovery if a significant abnormality is detected (or as clinically indicated)

Troponin (additionally other cardiac markers, i.e. AST/ALT and LDH depending on the investigators decision if clinically indicated) should also be assessed on identification of abnormal ECG findings, e.g. new repolarisation abnormalities. A repeat cardiac marker assessment should also be performed 24 hours later, if such findings occur, the same Troponin isoform should be assessed at each of the visits.

An ECG should be performed at any cardiac event with symptoms that may be due to cardiac ischaemia, or arrhythmia (such as chest pain or palpitations). An ECG will also be captured in all cases of dyspnoea and pulmonary oedema and additionally at the discretion of the investigator if clinically indicated.

7.3.4 CT scan

During the first 6 cycles of treatment patients must be assessed by contrast enhanced CT NCAP scan after every 2 cycles of treatment. Two dimensional measurements to calculate the sum of product diameter (SPD) must be taken.

Patients with stable disease or better will remain on study treatment After this time patients that remain on treatment will be assessed by contrast enhanced CT NCAP scan after every 4 cycles. Additional scans may be performed at any time if there is clinical suspicion of progression.

A Bone Marrow Trephine Biopsy should be performed for confirmation of either isolated disease progression within the bone marrow or to confirm complete remission if in CR on CT or PET.

If a patient discontinues treatment without progression they should also be assessed by contrast enhanced CT NCAP scan every 3-4 months for 1 year after their first treatment where possible. CT scans after 1 year will be as per standard practice or at progression (whichever is sooner).

High resolution (HR) CT of the chest should be performed if clinically indicated by pulmonary symptoms any time during the study. For any new respiratory symptoms (cough, dyspnoea, lower respiratory infection) not clearly explained by other factors (e.g., dyspnoea associated with substantial drop in haemoglobin), patients should have oxygen saturation measured. If oxygen saturation <92%, the HR CT Chest should be repeated and pulmonary function tests (PFTs) should be performed. For further information see section 7.5.5.

7.3.5 PET CT scan

A PET CT (contrast enhanced) scan should be performed at screening, following cycle 2 (within the day 17-21 treatment gap), and after cycle 6 (within the day 17-21 treatment gap) or progression if this is sooner.

The screening PET CT and the PET CT after 6 courses would be regarded as standard of care for the purposes of funding, in view of the international working group recommendations (1).

A contrast-enhanced CT scan should also be done, ideally at the same visit, at screening, after cycle 2 and cycle 6 to measure tumour volumes. This should be of diagnostic quality.

The UK NCRI PET research network will co-ordinate the quality control required to ensure accurate quantitation for PET scans (63). The Core Lab based at the KCL PET Centre at St Thomas' London will accredit PET centres prior to the study and be responsible for monitoring quality control during the trial and organise data transfer for central review.

All scans will be centrally reviewed at St Thomas' using the 5-point scale for visual interpretation (Deauville Criteria and the Lugano classification). Semi-quantitative analysis will also be performed using the published value for Δ SUVmax \geq 66% at 2 cycles to separate good from poor responders but receiver operating characteristic (ROC) curves will also be derived to determine if possible whether the optimal cut-off for patients treated with AZD2014 is similar to the cut-off for patients with DLBCL treated with (R)CHOP chemotherapy (35,38,39). Maximal standardized uptake value reduction is calculated as follows:

SUVmax reduction (%) = 100 x [SUVmax (PET0) - SUVmax (iPET)/SUVmax (PET screening)].

Standard contrast enhanced CT responses will be classified according to the International Workshop Criteria (1).

PET CT scans should therefore be sent to c/o Core Lab as St Thomas', For attention of [name] Clinical PET Centre, St Thomas', [name],

Please see the trial PET-CT manual for further details.

7.4 Sample Collection for research

7.4.1 Tumour paraffin blocks

For all patients a paraffin embedded block of tumour tissue will be collected within 3 months of trial entry. We also request an additional biopsy/tumour block at relapse.

There is also an optional biopsy on day 15 (+/- 2 days) of cycle 1 to assess for pharmacodynamic changes and allowing correlation with response.

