7.5.2.4 Recommendations for Treatment of Hyperglycaemia

Treatment related findings of elevated blood glucose levels should be reported as AE (s) if they fulfil the CTCAE criteria and SAE(s) if meeting the SAE reporting criteria.

In general management of hyperglycaemia should be performed according to local standards at the discretion of the Investigator.Due to the predicted short half-life of AZD2014, only a short period of hyperglycaemia with insulin resistance is expected. Therefore early treatment with high doses of insulin/and or oral anti-diabetes medication should be carefully evaluated and blood sugars and hypokalemia monitored as per standard clinical practice.

If blood glucose levels are < 250 mg/dl (Grade 2), generally no medical treatment is required. Dietary modification may be initiated.

For ≥ Grade 3 hyperglycaemia, dose modifications are required see Section 7.5.1

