7.8 Concomitant Medication

7.8.1 Concomitant treatment with CYP inhibitors, inducers and substrates

If a patient requires short-term administration of a restricted CYP3A4/5, Pgp or BCRP **inhibitor** AZD2014 treatment must be withheld for three days prior to administration and not restarted until the concomitant therapy has been discontinued for the appropriate time period described in Appendix 2.

If a patient requires short-term administration of a restricted CYP3A4/5, Pgp (MDR1) or BCRP isoenzyme **inducer** this should be clearly documented in the Case Report Form (CRF) and may then be permitted, but the Investigator will be informed that this could lead to lower levels of study drug and a potential reduction in clinical efficacy.

If a patient requires short term administration of restricted **substrates** of OATP1B1, OATP1B3, MATE1 or MATE2K AZD2014 treatment must be withheld for 3 days prior to the first administration and not restarted until the concomitant therapy has been discontinued for the appropriate time period *described in Appendix 3*.

Information on all concomitant treatments given during the study with reasons for the treatment should be recorded in the CRF. If medically feasible, patients taking regular medication other than those excluded from this study should be maintained on it throughout the study period.

The lists of CYP inhibitors, inducers and substrates are not exhaustive and the absence of a drug from these lists does not imply that its combination with AZD2014 is safe.

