12.2 Analysis of Outcome Measures

- Best overall response will be reported as the number and proportion of patients in each response category, and overall, during the first 6 cycles of treatment. In addition, best response observed after 6 cycles until the end of the trial will be reported by category and overall.
- The number and proportion of patients experiencing toxicity, including haematological and nonhaematological toxicity, will be reported with 95% confidence intervals.
- Time to event outcomes will be assessed using the method of Kaplan and Meier with point estimates presented at 6, 12, 24 and 36 months with 95% confidence intervals along with median survival time and confidence intervals. A Kaplan meier plot will be produced.
- The mean maximum % decrease during the first 6 cycles of treatment and overall will be reported with 95% confidence intervals

The biomarker study and PET scan analysis at present are exploratory.

There is little data on the expression of mTOR pathway proteins in DLBCL so the aim is to define expression in biopsy samples taken at relapse (or within 3 months). In collaboration with AstraZeneca, we will assess the expression of these proteins (p-S6, p-AKT, and p-4E-BP1) by immunohistochemistry (IHC). These will be measured at relapse, at subsequent progression, and in any tissue obtained at further optimal biopsy at 15 days. This will be initially assessed in 8 patients, with the potential to expand the analysis dependent on response data. We will then seek to determine a cut off which best predicts response to AZD2014, if indeed there is any correlation. Appropriate

statistical models (e.g. area under the curve, logistic regression) will be used to determine the cut off as detailed in the Statistical Analysis Plan.

Other ethically approved research may be performed on these samples if agreed by the trial management group.

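### The window for the cycle 1 pharmacodynamic biopsy permits sampling on the fourth and fifth drug-free days and sets no time relative to the dose

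*Protocol*

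**What the plan says.** Section 7.4.1 sets the timing and the purpose together: "There is also an optional biopsy on day 15 (+/- 2 days) of cycle 1 to assess for pharmacodynamic changes". It gives no hour and no position before or after a dose. Footnote q to the schedule in Section 7.3 names day 15 of cycle 1 with no window. Section 12.1.2 and the synopsis also name day 15 without a window, and both describe the sample as an on-treatment biopsy.

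On dosing, Section 7.2 states: "Two consecutive days of treatment will be followed by 5 days with no treatment each week". It then lists the days: "Treatment would therefore be on days 1, 2, 8, 9, 15, 16, 22 and 23 of each cycle of 28 days". Doses are twice daily, about 12 hours apart.

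On how long the drug lasts, the protocol gives no figure. Section 7.5.2.4 refers to "the predicted short half-life of AZD2014, only a short period of hyperglycaemia with insulin resistance is expected". Section 7.8.1 says that before a short course of a restricted inhibitor "AZD2014 treatment must be withheld for three days prior to administration".

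On use of the tissue, Section 12.2 plans immunohistochemistry for p-S6, p-AKT and p-4E-BP1 at relapse, at later progression and in any tissue from the 15-day biopsy. On numbers it says: "This will be initially assessed in 8 patients, with the potential to expand the analysis dependent on response data". The analysis is labelled exploratory.

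**The concern.** A pharmacodynamic biopsy is meant to show what the drug does to its target while the drug is acting. Here the permitted days straddle the end of a five-day gap and the start of the next dosing pair. One label, on treatment, therefore covers tissue taken during dosing and tissue taken several days after the last tablet.

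If phosphorylation recovers between dosing pairs, a sample from the gap would look like baseline. With no dose time attached, that result cannot be told apart from true lack of target engagement. The synopsis lists biomarkers of mTOR activity and of response, and possible resistance mechanisms, among the secondary objectives. In a set this small, one or two samples read the wrong way could change the description of the drug's effect.

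**Working it through.** **Inputs.** Biopsy on day 15 +/- 2 (Section 7.4.1). Two days on and five off, twice-daily doses about 12 hours apart (Section 7.2). No half-life is stated, so a range of 3 to 24 hours is assumed below.

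**Step 1: dosing calendar.** Dosing days are 7w + 1 and 7w + 2 for w = 0, 1, 2, 3. This gives 1, 2, 8, 9, 15, 16, 22, 23, which reproduces the list in Section 7.2. Days 10 to 14 are drug-free.

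**Step 2: biopsy window.** 15 - 2 = 13 and 15 + 2 = 17, so five days are permitted.

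| Day | Status | Days since last dosing day |
|---|---|---|
| 13 | drug-free | 13 - 9 = 4 |
| 14 | drug-free | 14 - 9 = 5 |
| 15, before the morning dose | not yet re-dosed | 15 - 9 = 6 |
| 15, after the morning dose | dosing day | 0 |
| 16 | dosing day | 0 (or 1 if before that morning's dose) |
| 17 | drug-free | 17 - 16 = 1 |

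Two of the five permitted days (13 and 14) lie four or five days after the last dosing day. Day 15 before the dose is a further possibility. Counted from the evening dose on day 9 to the morning of day 15, the interval is 5.5 days, or 132 hours.

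**Step 3: how much drug could remain.** From the evening of day 9, the morning of day 13 is 3.5 x 24 = 84 hours and the morning of day 14 is 4.5 x 24 = 108 hours. The fraction remaining is 2^(-hours / half-life).

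| Assumed half-life | Day 13 (84 h) | Day 14 (108 h) | Day 15 pre-dose (132 h) |
|---|---|---|---|
| 3 h | about 0% | about 0% | about 0% |
| 6 h | 0.006% | 0.0004% | about 0% |
| 12 h | 0.8% | 0.2% | 0.05% |
| 24 h | 8.8% | 4.4% | 2.2% |

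Across that range, at most about 9% of the drug remains on day 13. This describes drug, not pathway inhibition, whose duration in tissue the protocol does not give.

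**Step 4: which permitted days are usable in practice.** If biopsies are done only on weekdays (an assumption), the number of permitted days that fall on day 13 or 14 depends on the start day: Monday 0 of 3, Tuesday 1 of 4, Wednesday 2 of 5, Thursday 2 of 4, Friday 2 of 3. These are counts of available slots, not forecasts of when biopsies will be done. The pre-dose problem on day 15 arises for every start day.

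**The case against.** The case against has real weight.

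- **The target is a dosing day.** Every mention of the biopsy names day 15, and Section 7.3 already schedules a clinic visit and bloods then in cycle 1. That pulls biopsies towards day 15. The example in Section 7.2, "if treatment was started on a Monday in the first week", puts days 13 and 14 on a weekend. This stands against any claim about frequency. It does not remove the permission, and Monday is only an example.
- **Recovery of the pathway is not documented.** The remark on half-life has no number and sits in advice on hyperglycaemia. The three-day hold is a precaution against interactions, not evidence on phosphorylation. Section 1.1 reports reduced phosphorylation in paired biopsies from the phase 1 study without their timing. This stands: loss of signal by days 13-14 is plausible, not shown. It is also a reason to know the time since dose.
- **Existing records may suffice.** Fixed dosing days and the patient diaries of Section 7.6 should let days since last dose be worked out for a dated biopsy, and a sample manual exists that is not shown. This stands in part. The protocol does not say that clock times are captured, and without them a day-15 sample cannot be placed before or after the dose.
- **Little depends on it.** The biopsy is optional and the analysis exploratory. The response and tolerability rules are untouched. This stands and limits the weight of the point.

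A reader might infer that many samples would be off drug. An even spread over the window gives 2/5 = 40%, or 3/5 = 60% if every day-15 biopsy were pre-dose; applied to 8 patients that is 3.2 to 4.8 samples. The documents do not support this. An even spread contradicts a stated target day, and the 8 are patients assessed at several time points, not 8 day-15 biopsies.

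A reader might also extend the point to the PET scans, which fall in the gap. That timing is deliberate and explained in footnote k, Section 7.3: "ideally as close to the next administration of treatment i.e. days 20/21 to avoid the potential for inflammatory uptake of FDG". It is not an error.

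**Conclusion.** The point holds as a defect in what the window permits. Two of five permitted days are the fourth and fifth drug-free days, and a pre-dose sample on the target day is about 5.5 days after the last dose. Neither suits a sample described as on treatment and taken for pharmacodynamics.

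The calendar needs no assumption. The consequence, a false impression of no target inhibition, assumes that inhibition fades within four to six days. The short half-life makes that plausible, but the protocol does not establish it. The share of samples affected cannot be derived. The matter is confined to an optional, exploratory analysis, and is worth correcting because sampling time that was never captured cannot be recovered at analysis.

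**What to change.** - In Section 7.4.1, remove the pre-dose side of the window: biopsy after the morning dose on day 15, or on day 16. Allow day 17 only if it is analysed as one day post-dose.
- Use the same wording in footnote q of Section 7.3, in Section 12.1.2 and in the synopsis.
- Record the date and time of the biopsy and of the last AZD2014 dose before it.
- Analyse the three markers by time since last dose, and do not pool off-drug samples as on-treatment.

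The dosing schedule and the PET timing stay as they are. The cost is protocol and sample-manual wording plus date and time fields on the CRF. The downside is a tighter booking window, which may lose an occasional optional biopsy. With a Friday start, for example, day 16 is a Saturday and day 15 would be the only weekday slot.
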